2. SYNOPSIS

Sponsor: University of California, Los Angeles (UCLA)	
Investigational Products: 
 • aripiprazole lauroxil long-acting injectable (AL-LAI; ARISTADA®) • aripiprazole lauroxil NanoCrystal® Dispersion (AL-NCD; ARISTADA INITIO®) 	
Active Ingredient: aripiprazole lauroxil	
Study Title: Aripiprazole lauroxil for Preventing Psychotic Relapse After an Initial Schizophrenia Episode (APPRAISE)	
Study Center: UCLA	
Investigator: [name].	
Study Period (years): Estimated date first patient's consent: TBD Estimated date last patient's visit: TBD + 48 months	Phase of development: Phase 4
Objectives:	

Primary: The primary objective is to assess whether schizophrenia patients who recently experienced their first psychotic episode that are randomized to AL-LAI are less likely to experience a re-emergence of positive psychotic symptoms compared to those randomized to oral aripiprazole (ARI-ORAL).
 
Secondary: The secondary objectives are to:
 
 1. Examine differences in functional outcome between the two treatment groups. We anticipate that role functioning will improve more in the group randomized to AL-LAI than those assigned to the ARI-ORAL group. 2. Evaluate and compare the cognitive changes of the AL-LAI vs. ARI-ORAL group over the 12-month Treatment period. It is hypothesized that patients assigned to AL-LAI will demonstrate relatively better performance on a standardized measure of cognition than those assigned to ARI-ORAL. 
Exploratory: Additional exploratory objectives are to determine whether the two medication groups differ in other symptoms domains, adherence, and tolerability (eg, negative symptoms, suicidality, self-reported awareness of having a mental disorder, service engagement, sexual/prolactin-related side effects, treatment engagement, and quality of life).
	
Study Design/Methods: This is a single-site study with all assessments and treatment to take place at the UCLA Aftercare Research Program ([name]), which is a program that specializes in the treatment and study of individuals with a recent onset of schizophrenia. Patients entering the program will have extensive diagnostic and treatment evaluations, and eligible patients meeting diagnostic criteria will be invited to participate in a 12-month open-label randomized study comparing AL-LAI with ARI-ORAL. The flow for each patient after initial enrollment and evaluation will involve a Stabilization period of up to 90 days with at least the final 2 weeks on oral aripiprazole	

as the sole antipsychotic medication, after which the patients will be randomly assigned to treatment with either ARI-ORAL or AL-LAI for a 12-month Treatment period.

Overview of the Randomized Treatment Groups:

Patients successfully completing the Stabilization period will be randomized to one of two medications groups: converting from oral antipsychotic to AL-LAI vs continuing on (ARI-ORAL). Randomization will be automated by UCLA. Patients successfully completing the Stabilization period will be randomized to one of two medications groups: converting from oral antipsychotic to AL-LAI vs continuing on (ARI ORAL). Each treatment group will be further randomized to computerized cognitive training with or without aerobic exercise.

Randomization to AL-LAI: Initiation of AL-LAI will begin with a one-day initiation regimen (one intramuscular injection of 675 mg AL-NCD and one single-dose of 30 mg oral aripiprazole). Subsequent dosing of AL-LAI will be flexible based on clinician judgment. The first AL-LAI injection may be administered on the same day as the one-day initiation regimen or up to 10 days thereafter. Treatment with AL-LAI can be initiated at a dose of 441 mg, 662 mg or 882 mg; 441 mg administered monthly, 882 mg administered every 6 weeks or 1064 mg administered every two months.

Randomization to ARI-ORAL: Patients will continue with ARI-ORAL doses within the recommended oral dosage range for the treatment of schizophrenia (10-30mg/day) with the usual starting dosage of 10 mg/day. ARI-ORAL dosage will be flexible and dosage will be at the discretion of the treating psychiatrist. Patients assigned to this treatment arm will receive a written prescription for a 30-day supply along with a medication coupon so there will be no medication cost to the patient.

Discontinuation of Assigned Treatment

Both groups will remain on their assigned treatment for 12 months or discontinue their assigned medication early. The reason(s) for early discontinuation of initial antipsychotic will be recorded, including whether it is initiated by the clinician or patient, and whether it is efficacy or tolerability related. Patients will be assessed for the reason for discontinuation using a version of the All-Cause Discontinuation (ACD) measure that was the primary outcome of the CATIE schizophrenia study. If a switch to another antipsychotic medication is warranted, the new therapy will be determined by the prescribing psychiatrist's judgment using the medication selection recommendation adapted from NAVIGATE pharmacologic treatment manual developed as part of the Recovery After an Initial Schizophrenia Episode (RAISE) study intervention groups. Patients discontinuing study drug after Randomization, but remaining in active treatment and follow-up, may be prescribed any first-line oral antipsychotic within the prescribing information dosage for schizophrenia. Patients will be encouraged to stay in the study for the remainder of the 12-month Treatment period and will be administered all of the scheduled assessments even if the initial randomly assigned antipsychotic medication is discontinued by the treating psychiatrist.

Symptom assessments will occur every two weeks, functional endpoint will occur every three months, and the cognitive endpoint will occur at baseline and at the 6- and 12-month points. All patients participating in the protocol will be invited to concurrently participate in a separate NIMH-funded psychosocial intervention protocol comparing the effectiveness of computerized cognitive training with and without aerobic exercise training.

Number of Patients Planned: Approximately 128 patients enrolled into the Stabilization period for final randomized sample of 90 (45 in each group) with a target of 14 relapses

Main Criteria for Inclusion: Men and women aged 18 to 45 years, inclusive, with current diagnosis of schizophreniform disorder, schizophrenia, or schizoaffective depressed subtype disorder as defined by DSM-5 with the first psychotic episode having occurred within the last 24 months prior to Screening.
Reference Therapy, Dosage, Duration, and Mode of Administration: ARI-ORAL treatment will be initiated for all patients during the Stabilization period per the label recommended range for the treatment of schizophrenia ARI-ORAL will continue to be prescribed for patients randomly assigned to the ARI-ORAL group during the Treatment period. AL-LAI treatment will be initiated with the one-day initiation regimen (675 mg AL-NCD and 30 mg oral aripiprazole), but may alternatively be initiated with 21 consecutive days of supplementation with ARI-ORAL if clinically appropriate or preferable. The first AL-LAI injection may be administered on the same day as AL-NCD or up to 10 days thereafter as per clinical judgment. AL-LAI will be flexibly dosed for 12 months per label and can be initiated at a dose of 441 mg, 662 mg or 882 mg administered monthly, 882 mg administered every 6 weeks or 1064 mg administered every two months.
Duration of Study: ~15 months (3 months Stabilization period and 12 month Treatment period)
Criteria for Efficacy Evaluation: Primary Endpoint The primary endpoint will be time to first positive symptom exacerbation and/or relapse following a period of absence or relatively low levels of psychotic symptoms based on the expanded 24-item version Brief Psychiatric Rating Scale. Secondary Endpoints Functional assessment: The Role ratings on the Global Functioning Scale (GFS: Role) will serve as the measure of functional outcome. The GFS: ROLE will be administered every three months throughout the 12-month Treatment period. Cognitive assessment: The Overall Composite T-score from the MATRICS Consensus Cognitive Battery (MCCB) will be the overall index of cognitive performance. The MCCB will be administered every six months throughout the 12-month Treatment period. Exploratory Endpoints Endpoints include Quality of Life, negative symptoms, self-reported awareness of having a mental disorder, service engagement, prolactin-related side effects, treatment satisfaction, and family/caregiver medication administration burden. Safety Assessments Extrapyramidal symptoms will be assessed on three scales (Abnormal Involuntary Movement Scale, Barnes Akathisia Rating Scale, and the Extrapyramidal Symptom Rating Scale). Adverse events (including serious and AEs of special interest), and suicidality will be monitored.
Statistical methods: Sample Size Considerations: Ninety first-episode patients will be randomized (1:1) fashion to either AL-LAI or ARI-ORAL, and based on our previous RCT, assume a 20% attrition rate over 12 months. 45 randomized patients (36 completers) in each group provides at least 80% power. Statistical power considerations are based on the effect sizes observed when comparing long-acting injectable risperidone vs oral risperidone (survival analysis for psychotic relapse: 5% relapse in the risperidone long-acting injectable group and 33% relapse in the oral risperidone group). On the basis of hazard function rates of 5.0% (AL-LAI)

and 33% (ARI-ORAL), the study has 87% power ($\alpha=0.05$). On a more conservative basis of hazard function rates of 7.5% (AL-LAI) and 33% (ARI-ORAL), the study has 78% power ($\alpha=0.05$).

For the secondary hypothesis for the relative changes in the MCCB Composite score and the GFS: Role, we will use a two-sided significance level of $\alpha=0.025$ to account for type 1 error inflation. For the MCCB Composite score, assuming a within-patient correlation between repeated measurements of $r=0.89$ (based on a prior study), the proposed design provides us sufficient power (≥ 0.80) for Group X Time interaction effects as small as Cohen's $f=0.09$. Based on our previous work, we anticipate a medium effect size (Cohen's $f=0.25$ or $d=0.50$), and this design provides a power of >0.99 for an effect of this size. For the GFS rating, if we assume a within-patient correlation of $r=0.5$, with $\alpha=0.025$, our GLMM will have 80% power to detect an interaction corresponding to an effect size of $f=0.20$. Based on a prior study, we anticipate an effect size of $f=0.32$ or $d=0.63$ for the GFS: Role ratings, for which we would have $>99\%$ power.

Thus, for both primary and secondary outcome measures we will be able to detect differential treatment effects based on our proposed design and expected sample size.

Analysis of Efficacy:

The primary hypothesis is that the hazard function (i.e. the risk of an event per unit of time) of the two medication groups differs between AL-LAI and the ARI-ORAL group. The hypothesis will be examined in a Cox regression model on the time to first relapse. We will include medication group membership, participation status in the NIMH exercise study, and length of stabilization period as predictors in the model.

The secondary hypotheses of the MCCB composite score and the GFS (Role) rating will be examined in general linear mixed models (GLMMs). We will include participation status in the NIMH exercise study, medication group as a between-patient variable and time as a within-patient variable in the model, and time*group as a within-between interaction term. Additionally, we will include length of stabilization period as a person level time invariant covariate. The primary effect of interest is the difference in the pattern of change over time of the dependent variable between the medication groups (i.e. the time*group interaction term). GLMMs properly account for correlations induced by repeated measurements within patients and automatically handle missing data, producing unbiased estimates as long as observations are missing at random. The GLMM will use Satterthwaite's approximation to estimate degrees of freedom for the tests of the fixed and random effects, and model the variance-covariance matrix as a Toeplitz matrix. If this assumption does not lead to convergence we will instead use compound symmetry. The secondary analyses will compare the change in the MCCB Composite score and GFS (Role) ratings between the two medication groups over the 12-month study period.

The data analytic methods for the exploratory measures will in general parallel those of the secondary measures.

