12. STATISTICS

12.1.1. Sample Size Considerations

Ninety first-episode patients will be randomized (1:1) fashion to either AL-LAI or ARI-ORAL, and based on our previous RCT, assume a 20% attrition rate over 12 months. Statistical power considerations are based on the effect sizes observed when comparing long-acting injectable risperidone vs. oral risperidone (survival analysis for psychotic relapse: 5% relapse in the risperidone long-acting injectable group and 33% relapse in the oral risperidone group). On the basis of hazard function rates of 5.0% (AL-LAI) and 33% (ARI-ORAL), the study has 87% power ($\alpha=0.05$). On a more conservative basis of hazard function rates of 7.5% (AL-LAI) and 33% (ARI-ORAL), the study has 78% power ($\alpha=0.05$) (Table 6).

For the secondary hypothesis for the relative changes in the MCCB Composite score and the GFS: Role, we will use a two-sided significance level of $\alpha=.025$ to account for type 1 error inflation. For the MCCB Composite score, assuming a within-patient correlation between repeated measurements of $r=0.89$ (based on a prior study), the proposed design provides us sufficient power ($>=0.80$) for Group X Time interaction effects as small as Cohen's $f=0.09$. Based on our previous work, we anticipate a medium effect size (Cohen's $f=0.25$ or $d=0.50$), and this design provides a power of >0.99 for an effect of this size. For the GFS rating, if we assume a within-patient correlation of $r=0.5$, with $\alpha=0.025$, our GLMM will have 80% power to detect an interaction corresponding to an effect size of $f=.20$. Based on a prior study, we anticipate an effect size of $f=0.32$ or $d=0.63$ for the GFS: Role ratings, for which we would have $>99\%$ power.

Thus, for both primary and secondary outcome measures we will be able to detect differential treatment effects based on our proposed design and expected sample size.

Table 7: Power Calculations by Analysis with N=35 Each Group (N=28 at completion)

Clinical assumption for each group			Power	Alpha
Primary Analyses	Hazard ratio between the two groups	Difference in hazard functions similar to that of our previous RCT: Long-acting injectable: 5%, oral antipsychotic: 33%	87%	.05
		For rates of hazard function rates of 7.5% (AL-LAI) and 33% (ARI-ORAL)	78%	
Secondary Analyses: MCCB Overall Composite score	change from BL in MCCB Overall Composite score	Based on our previous work, we anticipate a medium effect size (Cohen's $f=.25$ or $d=.50$)	>99%	.025

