12.4. Efficacy Analysis

The primary hypothesis, that the hazard function (i.e. the risk of an event per unit of time) of the two medication groups differs between AL-LAI than the ARI-ORAL group, will be examined in a Cox regression analysis on the time to first relapse. We will include medication group membership, participation status in the NIMH exercise study, and length of stabilization period as predictors in the model.

For the secondary hypotheses involving the MCCB composite score, the GFS: (Role) we will use general linear mixed models (GLMMs). We will include participation status in the NIMH exercise study, medication group as a between-patient variable and time as a within-patient

variable in the model, and time*group as a within-between interaction term. Additionally, we will include length of stabilization period as person level time invariant covariate. The primary effect of interest is the difference in the pattern of change over time of the dependent variable between the medication groups, i.e. the time*group interaction term. GLMMs properly account for correlations induced by repeated measurements within patients and automatically handle missing data, producing unbiased estimates as long as observations are missing at random. The GLMM will use Satterthwaite's approximation to estimate degrees of freedom for the tests of the fixed and random effects, and model the variance-covariance matrix as a Toeplitz matrix. If this assumption does not lead to convergence we will instead use compound symmetry. The secondary analyses will compare the change in the MCCB Composite score and GFS: (Role) ratings between the two medication groups over the 12-month study period.

The data analyses for the exploratory measures will parallel those of the secondary measures.

All statistical tests and confidence intervals, unless stated otherwise, will be two-sided and will be set at $\alpha=0.05$.

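### The Synopsis claims at least 80% power for 45 per group, but the plan's own conservative case is 78%; the inputs are mislabelled as hazard rates, no power method is named, and Table 7 attaches the same powers to a smaller sample

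*Combined protocol and SAP*

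**What the plan says.** The Synopsis, under Sample Size Considerations, fixes 1:1 randomisation of 90 patients and tells the reader to "assume a 20% attrition rate over 12 months". It then says that "45 randomized patients (36 completers) in each group provides at least 80% power".

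The inputs come from an earlier trial of injectable versus oral risperidone, described as "survival analysis for psychotic relapse: 5% relapse in the risperidone long-acting injectable group and 33% relapse in the oral risperidone group". The next sentences of the Synopsis, repeated in Section 12.1.1, recast these figures as hazards: "On the basis of hazard function rates of 5.0% (AL-LAI) and 33% (ARI-ORAL), the study has 87% power", and then "On a more conservative basis of hazard function rates of 7.5% (AL-LAI) and 33% (ARI-ORAL), the study has 78% power". Section 12.1.1 does not repeat the sentence about at least 80%.

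The primary hypothesis "will be examined in a Cox regression analysis on the time to first relapse" (Section 12.4), with medication group, NIMH study participation and length of stabilisation as predictors. Section 12.4 makes tests two-sided at 0.05 unless stated otherwise. Both the Synopsis and Section 12.4 define a hazard as the risk of an event per unit of time.

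Table 7 in Section 12.1.1 shows 87% and 78% again, in a row labelled as a hazard ratio, under a heading that gives 35 per group and 28 at completion. Neither the text nor the table names a power formula or a test.

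**The concern.** There are four defects in a short stretch of text.

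- The one sentence that justifies the sample size is unqualified, and a figure in the same paragraph contradicts it.
- The inputs change from relapse percentages to hazard rates without any change in value. Under the plan's own definition of a hazard these are different quantities, and the choice changes the power.
- With no method named, a reader cannot tell whether 87% and 78% describe the planned Cox analysis of everyone randomised or a simpler comparison among completers.
- Table 7 gives the same powers for a smaller sample than the text does.

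At stake is whether the printed power can be checked and attached to the primary test. The number of patients is not at stake.

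**Working it through.** **Inputs.** 45 randomised per group; 20% attrition, so 45 × 0.80 = 36 completers (Synopsis). Relapse of 5% or 7.5% versus 33% (Synopsis, 12.1.1). Two-sided α = 0.05 (12.4), z = 1.96. Table 7: 35 × 0.80 = 28 completers.

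**1. The plan's own figures.** For a pooled two-proportion test with n per arm, p̄ = (p₁ + p₂)/2 and d = p₂ − p₁:

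power = Φ{[d√n − 1.96·√(2p̄(1 − p̄))] / √(p₁(1 − p₁) + p₂(1 − p₂))}

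- 5% vs 33%, n = 36: p̄ = 0.19; (0.28 × 6 − 1.96 × 0.5548)/0.5183 = 1.14; power 87.4%.
- 7.5% vs 33%, n = 36: p̄ = 0.2025; (0.255 × 6 − 1.96 × 0.5683)/0.5390 = 0.77; power 78.0%.

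Both round to the stated values. By this formula the conservative case needs 38 evaluable per arm for 80%; the plan has 36.

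**2. Survival formulas on all 45 per arm.** Assume constant hazards and exponential dropout. Yearly hazards: −ln(0.95) = 0.0513, −ln(0.925) = 0.0780, −ln(0.67) = 0.4005; dropout −ln(0.80) = 0.2231. Hazard ratios: 0.0513/0.4005 = 0.128 and 0.0780/0.4005 = 0.195. The probability of an observed relapse is λ/(λ + 0.2231) × [1 − exp(−(λ + 0.2231))], which gives 0.0449, 0.0673 and 0.2980. Expected relapses: 45 × (0.0449 + 0.2980) = 15.4 and 45 × (0.0673 + 0.2980) = 16.4.

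- Freedman, Φ{√E·(1 − HR)/(1 + HR) − 1.96}: 85.9% and 78.0%.
- Lachin-Foulkes exponential survival: 87.1% and 79.3%.
- Schoenfeld, Φ{√(E/4)·|ln HR| − 1.96}: 98.1% and 91.3%.

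The first two come within about 2 points of 87% and 78%; Schoenfeld does not. Only the two-proportion result at 36 completers rounds to both stated figures.

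**3. The planned type of test.** Simulation with 45 per arm under the assumptions of step 2, unadjusted, 6,000 trials per case:

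| Test | 5% vs 33% | 7.5% vs 33% |
|---|---|---|
| Log-rank | about 93% | about 85% |
| Cox, likelihood ratio | about 94% | about 86% |
| Cox, Wald | about 78% | about 77% |

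The Wald test falls behind partly because in about 12% of base-case trials one arm has no relapse, so the estimate diverges; such trials were counted as not significant.

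**4. The label.** Read literally as yearly hazards, 0.05, 0.075 and 0.33 give relapse of 1 − exp(−0.05) = 4.9%, 1 − exp(−0.075) = 7.2% and 1 − exp(−0.33) = 28.1%. The formula of step 1 at n = 36 then gives 77% and 65%. The stated figures are therefore recovered by treating the inputs as proportions, not as hazards.

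**5. Table 7.** The formula of step 1 at n = 28:

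- 5% vs 33%: (0.28 × 5.2915 − 1.0874)/0.5183 = 0.76; power 77.7%.
- 7.5% vs 33%: (0.255 × 5.2915 − 1.1139)/0.5390 = 0.44; power 66.9%.

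The table prints 87% and 78%.

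**The case against.** The contradiction is 2 points wide, appears only in the Synopsis, and is followed at once by both scenario powers, so nobody is misled for long. The base case taken from the earlier trial satisfies the sentence. Section 12.1.1 leaves the sentence out. All of that stands, and it limits the point to a correction of text.

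The plan also speaks of survival analysis and hazards throughout and never mentions a two-proportion test. A reader might infer that 87% and 78% can have come only from a completer two-proportion calculation. The documents do not support that: two standard survival formulas on all randomised patients land within about 2 points. The completer calculation is the closest match and fits the Synopsis's mention of 36 completers, but it remains an inference about an unstated method.

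Three further readings are tempting and also fail.

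- That the Cox analysis is underpowered. The unadjusted simulations run from about 77% to about 94%, depending on the scenario and on which test is read from the model; the plan does not say which.
- That 78% is a floor. The Wald result in the conservative case is slightly lower.
- That the trial would fall short of its target of 14 relapses. This needs the literal-hazard reading, and on that reading 11.9 and 12.7 relapses arise only if the 72 completers alone are counted. Counting all 90 with 20% dropout gives about 13.4 and 14.3. Read as relapse proportions, the inputs give 15.4 and 16.4. Section 6.4 also provides for enrolling beyond 90 to secure 14.

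**Conclusion.** The point holds as a reporting error with four parts.

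- The claim of at least 80% is true for 5% versus 33% (87%) and false for the plan's own conservative case (78%).
- Relapse proportions are mislabelled as hazard rates. Taking the label at its word would cut the power by the completer formula to 77% and 65%.
- The power method is not stated. A two-proportion test on 36 completers matches exactly, so the figures appear to be a completer calculation rather than one for the planned Cox analysis, but this is not proven.
- The Table 7 heading does not fit the text. At its 28 completers the matching formula gives 77.7% and 66.9%, which is 9 and 11 points below what the table prints.

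The survival results assume constant hazards, exponential dropout of 20% over 12 months, no covariates, and 5%, 7.5% and 33% read as cumulative relapse at 12 months. The documents do not state the time horizon of the earlier trial's percentages; 12 months is taken from this trial's Treatment period. Neither the sample size nor the choice of primary analysis is called into question.

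**What to change.** In the Synopsis, limit the sentence on at least 80% to the 5% versus 33% case, or replace it with: 87% for 5% versus 33% and 78% for 7.5% versus 33%.

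In the Synopsis, Section 12.1.1 and Table 7:

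- Call 5%, 7.5% and 33% 12-month relapse proportions, and add that they correspond to hazard ratios of about 0.13 and 0.19 under constant hazards.
- Name the method behind 87% and 78%. If it was a two-proportion test on completers, say so. Otherwise restate power for a named test on all randomised patients, with its assumptions: about 93% and 85% for the log-rank test (the Cox likelihood-ratio test is within about 1 point), or about 78% and 77% for the Cox Wald test. If power is restated, say in Section 12.4 which test of the medication effect is used.
- Change the Table 7 heading from 35 (28 at completion) to 45 (36 at completion).

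The cost is a few lines of text and confirmation from the study statistician of the method used. Enrolment and data collection do not change.

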Secondary Analyses: GFS Role Functioning	Change from BL in GFS Role Functioning	Based on a prior RCT, we anticipate an effect size of $f=.32$ or $d=.63$ for the GFS: Role ratings.	>99%	.025

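### The secondary mixed models compare change scores rather than adjusting for the Day 1 score, a valid but inefficient choice that costs GFS: Role precision (25% at Month 12 on the plan's assumed r=0.5) and MCCB little.

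*Combined protocol and SAP*

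**What the plan says.** The Synopsis (Analysis of Efficacy) describes one model for both secondary endpoints. It has "medication group as a between-patient variable and time as a within-patient variable in the model, and time*group as a within-between interaction term", plus participation status in the NIMH study. It adds that "we will include length of stabilization period as a person level time invariant covariate". Section 12.4 gives the same model, again with medication group as a "variable in the model, and time*group as a within-between interaction term". These are all the fixed effects named. The Day 1 score is not among them, and no common-baseline constraint is stated.

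On the quantity tested, the Synopsis says: "The primary effect of interest is the difference in the pattern of change over time of the dependent variable between the medication groups". Table 7 in section 12.1.1 labels the functional outcome "Change from BL in GFS Role Functioning". The plan will "model the variance-covariance matrix as a Toeplitz matrix", with compound symmetry if that does not converge.

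The precision assumptions are in the Synopsis and section 12.1.1. MCCB has a within-patient correlation of 0.89 from a prior study. For GFS: Role the wording is "if we assume a within-patient correlation of" 0.5. Both endpoints are tested two-sided at 0.025. Table 2 schedules both scores at Day 1, labelled the randomisation baseline. GFS: Role then has four follow-up visits (Months 3, 6, 9 and 12) and MCCB two (Months 6 and 12). Exploratory scales are to follow the same approach.

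**The concern.** When Day 1 is one level of time, a medication-group main effect is a free baseline difference between the arms. Randomisation makes the expected baseline means equal for a score taken before assignment, so that parameter estimates something known to be zero. With complete data the time*group term then reduces to differences in change from Day 1: the baseline is subtracted with weight 1, whereas the efficient weight is r.

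The plan does not say outright that Day 1 is a level of time, but the change wording implies it. If Day 1 were left out, it would not be used at all, and the post-baseline time*group term would miss a benefit that was already present at the first follow-up and stayed constant. Neither reading adjusts for Day 1.

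At stake is power for GFS: Role, one of only two secondary endpoints, in a small trial. With 45 per arm the chance baseline difference has a standard error of sqrt(2/45) = 0.21 SD. Section 7.4.13 states that severity of psychosis is not a stratification variable. A change score subtracts the whole of any such imbalance and so over-corrects when r is below 1.

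**Working it through.** **Inputs.** r=0.5 for GFS: Role and r=0.89 for MCCB; two-sided alpha 0.025; 45 randomised and 36 completers per arm; 20% attrition (Synopsis and section 12.1.1). Five GFS: Role visits and three MCCB visits, counting Day 1 (Table 2).

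**The plan's own figures.** I used the usual within-between interaction F test, with noncentrality f²·N·m/(1-r) and degrees of freedom m-1 and (N-2)(m-1).
- MCCB, at least 80% at f=0.09: reproduced (81.8% with N=56, m=3).
- GFS: Role, above 99% at f=0.32: reproduced (99.3% or more for N=56 or 72 and m=2, 3 or 5).
- GFS: Role, 80% at f=0.20 with r=0.5: not reproduced. N=72 gives 86.2%, 93.8% and 99.0% for m=2, 3 and 5; N=56 gives 75.2%, 85.3% and 95.7%.

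That mismatch is a separate matter, as is the conflict between Table 7's title (35 per arm, 28 completers) and the text (45 and 36). The variance ratio below does not depend on N.

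**Variance at one follow-up visit, complete data** (units of outcome variance):
- Change score: 2(1-r)
- Day 1 adjusted or common baseline: 1-r²
- Ratio: (1-r²)/[2(1-r)] = (1+r)/2, so the share saved is (1-r)/2

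| Endpoint | Change | Adjusted | Variance saved |
|---|---|---|---|
| GFS: Role, r=0.5 | 2(0.5) = 1.00 | 1-0.25 = 0.75 | 25% |
| MCCB, r=0.89 | 2(0.11) = 0.220 | 1-0.792 = 0.208 | 5.5% |

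For GFS: Role the standard error falls by 1-sqrt(0.75) = 13.4%. Thirty-six adjusted patients per arm are worth 36/0.75 = 48 unadjusted.

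**Dropout.** Generalised least squares, 45 per arm, 20% monotone dropout:
- GFS: Role, Month 12: ratio 0.785 under compound symmetry (21.5% saved), or 0.779 if correlation decays with a Day 1 to Month 12 value of 0.5 (22.1% saved).
- GFS: Role, linear trend: 25% saved with complete data and 23% with dropout (compound symmetry).
- MCCB, Month 12: ratio 0.954 (about 5% saved).

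**Sensitivity to r (Month 12, complete data).** At r=0.3 the saving is 35%; at r=0.7 it is 15%. If 0.5 held only between adjacent visits and decayed, the Day 1 to Month 12 correlation would be 0.5⁴ = 0.0625 and the saving (1-0.0625)/2 = 47%.

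**The 4-df time*group test** (time categorical, compound symmetry, r=0.5, complete data, 36 per arm, maximum difference 0.63 SD):

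| Shape of effect | Noncentrality lost | Power, planned to constrained |
|---|---|---|
| Month 12 only | 4% | 68% to 70% |
| Steady ramp | 25% | 54% to 70% |
| Immediate and constant | 40% | 68% to 92% |

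**Month 12 contrast power, GFS: Role** (noncentral t, 36 per arm, SE 0.236 against 0.204 SD). At 0.63 SD: 65% to 79%. At 0.50 SD: 44% to 57%. Here d is read as the Month 12 difference divided by the outcome SD; the plan does not define it.

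**Other covariates.** NIMH status and stabilization length enter as main effects only. With complete data they do not sharpen time*group, so they do not recover the loss.

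**The case against.** A group-by-time mixed model is standard, and unbiased under its stated assumptions. The primary Cox analysis is untouched. That stands: this is an efficiency point on secondary and exploratory endpoints. A reader might infer that the planned test is biased or has the wrong type I error; nothing in the documents supports that. Nor is Day 1 discarded. It is used, with weight 1.

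A reader might also take 25% as the loss in the planned test. That figure belongs to the Month 12 or linear-trend contrast with complete data and r=0.5. The plan names the time*group term, where the loss depends on effect shape, and r=0.5 is an assumption, not an estimate. The 65% is likewise no contradiction of the plan's figure above 99%, which uses a different effect-size definition (f=0.32 over all visits).

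The strongest objection concerns the remedy. Section 12.2.1 defines the ITT set as AL-LAI patients with at least one dose and ARI-ORAL patients with at least one filled prescription after assignment. That filter acts after randomisation and differs by arm, in an open-label trial. Equal baseline means are guaranteed only for everyone randomised. If selection shifted one arm by b at every visit, the change contrast would cancel it, while the adjusted contrast would keep (1-r)b, or half of b at r=0.5. The size of b is unknown and may be small, but it would be wrong to call adjustment free of any downside here.

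**Conclusion.** The point holds as one of lost efficiency. The planned models are valid but leave precision unused. On the plan's r=0.5, adjustment would remove 25% of the GFS: Role variance at Month 12 with complete data, and about 21% to 23% for the Month 12 or linear-trend contrast with 20% dropout. For the omnibus interaction the gain runs from about 4% to 40% over the three effect shapes examined. For MCCB it is about 5%, which hardly matters.

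These sizes rest on three conditions: Day 1 is a level of time in the planned model, the assumed r applies between Day 1 and the follow-up visit, and Day 1 scores are taken before assignment. Section 7.1 places baseline testing in the Stabilization period, which supports the last, but it should be confirmed. The change is worth making because it is cheap and GFS: Role has the lower assumed correlation.

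**What to change.** In section 12.4 and the Synopsis, choose one of two forms.

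1. Keep Day 1 as a response, drop the medication-group main effect so that both arms share one Day 1 mean, and keep time and the post-baseline time*group terms.
2. Analyse post-baseline visits with Day 1 score and Day 1 score*visit as covariates. Test the treatment contrast itself, at Month 12 or over all post-baseline visits. Testing only the post-baseline interaction would miss a constant effect.

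The two are similar but not identical under the planned Toeplitz or compound symmetry covariance with dropout, so the plan should name one. It should also state which contrast is the test, and confirm that Day 1 scores precede assignment.

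Fit the model on everyone randomised. If the section 12.2.1 set is kept, report the unconstrained model as a sensitivity analysis. Use the same form for exploratory scales that have a Day 1 score.

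The cost is SAP wording and one model statement, with no new assessments. The common-baseline assumption, and its limit in a filtered set, should be written down.
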